6.1. Definitions

6.1.1. Adverse Event. An adverse event (AE) is any symptom, sign, illness or experience that develops or worsens in severity during the course of the study. Intercurrent illnesses or injuries should be regarded as adverse events. Abnormal results of diagnostic procedures are considered to be adverse events if the abnormality:

- results in study withdrawal
- is associated with a serious adverse event
- is associated with clinical signs or symptoms
- leads to additional treatment or to further diagnostic tests
- is considered by the investigator to be of clinical significance

6.1.2. Serious Adverse Event. Adverse events are classified as serious or non-serious. A serious adverse event is any AE that is:

- fatal
- life-threatening
- requires or prolongs hospital stay
- results in persistent or significant disability or incapacity
- a congenital anomaly or birth defect
- an important medical event

Important medical events are those that may not be immediately life threatening, but are clearly of major clinical significance. They may jeopardize the subject, and may require intervention to prevent one of the other serious outcomes noted above. For example, drug overdose or abuse, a seizure that did not result in in-patient hospitalization, or intensive treatment of bronchospasm in an emergency department would typically be considered serious. All adverse events that do not meet any of the criteria for serious will be regarded as non-serious adverse events.

6.1.3. Adverse Event Reporting Period. Adverse events will be reported if they occur between the time that informed consent is granted through 30 days following the last study visit.

6.1.4. Post-study Adverse Event. All unresolved adverse events will be followed by the PI until the events are resolved, the subject is lost to follow-up, or the adverse event is otherwise explained. At the last scheduled visit, the investigator will instruct each subject to report any subsequent event(s) that the subject, or the subject's personal physician, believes might reasonably be related to participation in this study. The investigator will notify the study sponsor of any death or adverse event occurring at any time after a subject has discontinued or terminated study participation that may reasonably be related to this study. The sponsor will also be notified if the investigator should become aware of the development of cancer or of a congenital anomaly in a subsequently conceived offspring of a subject that has participated in this study.

6.1.5. Abnormal Laboratory Values. A clinical laboratory abnormality will be documented as an adverse event if any one of the following conditions is met:

- The laboratory abnormality is not otherwise refuted by a repeat test to confirm the abnormality
- The abnormality suggests a disease and/or organ toxicity
- The abnormality is of a degree that requires active management; e.g. change of dose, discontinuation of the drug, more frequent follow-up assessments, further diagnostic investigation, etc.

6.1.6. Hospitalization, Prolonged Hospitalization or Surgery. Any adverse event that results in hospitalization or prolonged hospitalization will be documented and reported as a serious adverse event unless specifically instructed otherwise in this protocol. Any condition responsible for surgery will be documented as an adverse event if the condition meets the criteria for an adverse event. Neither the condition, hospitalization, prolonged hospitalization, nor surgery are reported as an adverse event in the following circumstances:

- Hospitalization or prolonged hospitalization for diagnostic or elective surgical procedures for a preexisting condition. Surgery should not be reported as an outcome of an adverse event if the purpose of the surgery was elective or diagnostic and the outcome was uneventful.
- Hospitalization or prolonged hospitalization required to allow efficacy measurement for the study.
- Hospitalization or prolonged hospitalization for therapy of the target disease of the study, unless it is a worsening or increase in frequency of hospital admissions as judged by the clinical investigator.

6.2. Recording of Adverse Events. At each contact with the subject, the investigator will seek information on adverse events by specific questioning and, as appropriate, by examination. Information on all adverse events will be recorded immediately in the source document, and also in the appropriate adverse event module of the case report form. All clearly related signs, symptoms, and abnormal diagnostic procedures results will be recorded in the source document. All adverse events occurring during the study period will be recorded. The clinical course of each event will be followed until resolution, stabilization, or until it has been determined that the study treatment or participation is not the cause. Serious adverse events that are still ongoing at the end of the study period will be followed up to determine the final outcome. Any serious adverse event that occurs after the study period and is considered to be possibly related to the study treatment or study participation will be recorded and reported immediately.

6.3. Reporting of Serious Adverse Events. Reports of all serious adverse events with a reasonable possibility of being related to the study (including follow-up information) will be submitted to the IRB, according to the IRB policy, within 10 working days. Copies of each report and documentation of IRB notification and receipt will be kept in the Clinical Investigator's binder. Adverse events with a reasonable possibility of being related to the study which are not serious will be reported to the IRB as components of annual reports. Because this is an observational study, no data safety and monitoring board will be created for this trial. Adverse events and recruitment will be monitored by the PI and reported to the IRB, as described above.

7. Data Handling and Record Keeping

7.1. Confidentiality. Information about study subjects will be kept confidential and managed according to the requirements of the Health Insurance Portability and Accountability Act of 1996 (HIPAA). Those regulations require a signed subject authorization informing the subject of the following:

- What protected health information (PHI) will be collected from subjects in this study
- Who will have access to that information and why
- Who will use or disclose that information
- The rights of a research subject to revoke their authorization for use of their PHI.

In the event that a subject revokes authorization to collect or use PHI, the investigator, by regulation, retains the ability to use all information collected prior to the revocation of subject authorization. For subjects that have revoked authorization to collect or use PHI, attempts will be made to obtain permission to collect at least vital status (i.e. that the subject is alive) at the end of their scheduled study period.

7.2. Records Retention. All study data will be de-identified and stored in secured electronic files and/or a locked file cabinet within a locked room. Data including personal identifiers (i.e. screening data) will be kept separately in a secure, locked location.

8. Study Monitoring, Auditing, and Inspecting

8.1. Study Monitoring Plan. The PI will allocate adequate time for such monitoring activities. The PI will also ensure that any sponsor or other compliance or quality assurance reviewer is given access to all the above noted study-related documents and study related facilities (e.g. diagnostic laboratory), and has adequate space to conduct a monitoring visit, if requested.

8.2. Auditing and Inspecting. The PI will permit study-related monitoring, audits, and inspections by the IRB, the sponsor, government regulatory bodies, and compliance and quality assurance groups of all study related documents (e.g. source documents, regulatory documents, data collection instruments, study data etc.). The PI will ensure the capability for inspections of applicable study-related facilities (e.g. pharmacy, diagnostic laboratory, etc.).

9. Ethical Considerations

This protocol and any amendments will be submitted to the IRB, in agreement with local legal prescriptions, for formal approval of the study conduct. The decision of the IRB concerning the conduct of the study will be made in writing to the investigator and a copy of this decision will be provided to the sponsor before commencement of this study. All subjects for this study will be provided a consent form describing this study and providing sufficient information for subjects to make an informed decision about their participation in this study. The formal consent of a subject, using the IRB-approved consent form, must be obtained before that subject is submitted to any study procedure. This consent form must be signed by the subject or legally acceptable surrogate, and the investigator-designated research professional obtaining the consent.

10. Study Finances

10.1. Funding Source. This study is financed by the American Diabetes Association (Grant 4-14-CKD-20) and supplies are furnished by Medtronic.

10.2. Conflict of Interest. Any investigator who has a conflict of interest with this study (patent ownership, royalties, or financial gain greater than the minimum allowable by their institution, etc.) must have the conflict reviewed by a properly constituted Conflict of Interest Committee with a Committee-sanctioned conflict management plan that has been reviewed and approved by the study sponsor prior to participation in this study. All investigators will follow the Institutional conflict of interest policy.

10.3. Subject Payments. Participants will be compensated \$25 for each main study visit (study visits 1-5), for a total of \$125 if all study visits are completed.

10.4. Publication Plan. Funding sources will be acknowledged in publications, but funding sources will not be involved in decisions regarding what or how to publish study results in any way.

11. References

3. American Diabetes A. Standards of medical care in diabetes--2014. *Diabetes Care* 2014;37 Suppl 1:S14-80.
4. KDOQI Clinical Practice Guidelines and Clinical Practice Recommendations for Diabetes and Chronic Kidney Disease. *Am J Kidney Dis* 2007;49:S12-154.
6. de Boer IH, Rue TC, Hall YN, Heagerty PJ, Weiss NS, Himmelfarb J. Temporal trends in the prevalence of diabetic kidney disease in the United States. *JAMA : the journal of the American Medical Association* 2011;305:2532-9.
7. US Renal Data System, USRDS 2010 Annual Data Report; *Atlas of Chronic Kidney Disease and End-Stage Renal Disease in the United States*. Bethesda, MD2010.

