3.5 Intervention Throughout the 8 weeks (total) of this trial, we will ask all participants to discontinue use of their prevalent SU but maintain other glucose-lowering medications (e.g. insulin) at unchanged doses. We will then prescribe linagliptin for 4 weeks and glipizide for 4 weeks, in a randomly determined order. DPP-4 inhibitors are an attractive class of medications to lower blood glucose among patients at high risk of hypoglycemia because they enhance the actions of endogenous insulin, with little effect on insulin secretion or action when a source of oral glucose is absent. DDP-4 inhibitors may also have beneficial effects on microvascular complications, including CKD, independent of glucose.^{67,68} Linagliptin is particularly attractive for patients with CKD because it is primarily eliminated through non-renal routes and does not require dose adjustment or increased monitoring for adverse effects, even with advanced CKD.^{64,65} We will administer linagliptin at its standard fixed dose of 5 mg daily. For comparison, we will administer glipizide at a fixed dose of 5 mg daily. We selected glipizide because it has a relatively short half-life and is therefore commonly used in patients with CKD. While individuals will differ in their hypoglycemic responses to these medications and doses, we anticipate that mean glycemia will change to a similar extent with each intervention when averaged across participants. In addition, we will adjust for mean CGM blood glucose when comparing differences in hypoglycemia and glucose variability.

3.5.1 Randomization Each participant will be prescribed linagliptin for 4 weeks and glipizide for 4 weeks. The order of these interventions will be randomly assigned by the Northwest Kidney Center Pharmacy, which will dispense all study medications. There will be no stratification or blocking.

3.5.2 Blinding Participants will not be blinded to treatment assignment in order to reduce cost and maximize patient safety. However, data for the primary study outcome (time in range measured by CGM) will be masked to participants, and study staff and investigators will be given only coded treatment assignments (“A” and “B”) until data analyses are completed. In this setting, lack of participant blinding is unlikely to bias results.

4. Study procedures.

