4.6. Schedule of study measurements. This study consists of one screening visit and 5 study visits. Additional telephone and in-person contacts may be scheduled as needed to trouble-shoot or repeat CGM.

4.6.1. Screening Visit. The screening visit will last less than an hour and will assess eligibility criteria for the study. During the visit, informed consent will be administered by the study staff. The visit will include a focused medical history including review of the electronic medical record, an inventory of current and recent medications, and a blood draw to determine eligibility if necessary. If subjects have participated in the CANDY study, eligibility will be determined at the end of the CANDY study, and measurements used for that study may be used to determine eligibility.

4.6.2. Study Visit 1 At the first study visit, a complete medical history and medication inventory will be taken. The subject will be administered a medical history questionnaire. Height, weight and vital signs (blood pressure, heart rate) will be taken. The subject will be assigned the order of study medications and the first medication will be prescribed. The subject will pick up their first medication from the pharmacy and begin taking the medication. Adverse effects will be assessed.

4.6.2. Study Visit 2 At the second study visit, the CGM device will be introduced by the study staff. They will explain its purpose and functions in detail, place the CGM device, and thoroughly describe plans for trouble-shooting the CGM device. The study staff will also provide a study glucose meter and test strips for self-monitored blood glucose (SMBG) testing, explain expectations for tracking SMBG at home, provide logs for SMBG, and demonstrate proper use of the logs. Adverse effects will be assessed.

4.6.3. Study Visit 3 At the third study visit, the CGM device will be removed from the subject by the study staff, and the SMBG log will be turned in to the study staff. The subject will cease taking the first study medication on this day, and return any remaining prescription to the study staff. The visit will include a blood draw, and spot urine collection. The subject will pick up their second medication from the pharmacy and begin taking the medication the following morning. Adverse effects will be assessed.

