4.6.4. Study Visit 4 At the fourth study visit, the CGM device will be reintroduced by the study staff. They will place the CGM device, and thoroughly describe plans for trouble-shooting the CGM device. The study staff will also provide a study glucose meter and test strips for self-

monitored blood glucose (SMBG) testing, explain expectations for tracking SMBG at home, provide logs for SMBG, and demonstrate proper use of the logs. Adverse effects will be assessed.

4.6.5. Study Visit 5 At the fifth study visit, the CGM device will be removed from the subject by the study staff, and the SMBG log will be turned in to the study staff. The subject will cease taking the second study medication on this day, and return any remaining prescription to the study staff. The visit will include a blood draw, and spot urine collection. Adverse effects will be assessed.

24-hour contact information will be given to all participants for questions that arise during the CGM periods. Participants who do not complete at least 4 days of CGM will be asked to repeat measurements or will be replaced by an alternate participant

Table 3. Schedule of Procedures

Procedure	Screening	Visit 1	Visit 2	Visit 3	Visit 4	Visit 5
Informed Consent	X					
Medication inventory	X					
Medical History	X	X				
Blood draw	*X			X		X
Medical History Questionnaire		X				
Physical measurements (height, weight, vital signs)		X				
Randomization		X				
Medication Prescribed		X		X		
Urine-spot				X		X
CGM Provided			X		X	
CGM Returned				X		X
Log provided			X		X	

Log returned				X		X
AE		X	X	X	X	X

* Blood draw at the screening visit will be completed only if creatinine and hemoglobin A1c values are not otherwise available within 90 days prior to the screening visit.

5. Statistical analysis

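### All adverse events are reportable for 30 days after the last visit, but no scheduled procedure finds new ones after Visit 5 and participants are told to report only those thought related

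*Combined protocol and SAP*

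**What the plan says.** Four parts of the protocol bear on this point.

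- **Reporting window (6.1.3).** "Adverse events will be reported if they occur between the time that informed consent is granted through 30 days following the last study visit". There is no limit by seriousness or relatedness.
- **Schedule (4.6 and Table 3).** "This study consists of one screening visit and 5 study visits". The AE row of Table 3 is marked at Visits 1 to 5, and the table has no later column. Extra contacts are optional and serve another purpose: "Additional telephone and in-person contacts may be scheduled as needed to trouble-shoot or repeat CGM". At Visit 5 (4.6.5), "The subject will cease taking the second study medication on this day".
- **After the last visit (6.1.4).** Participants are asked to "report any subsequent event(s) that the subject, or the subject's personal physician, believes might reasonably be related to participation in this study". The investigator also follows unresolved events, notifies the sponsor of later deaths or events that may be related, and passes on any cancer or congenital anomaly that comes to light.
- **Recording (6.2).** "At each contact with the subject, the investigator will seek information on adverse events by specific questioning". Every event in the study period is to be recorded. After that period, the rule covers serious events considered possibly related. The study period is not defined.

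**The concern.** The window in 6.1.3 and the means of filling it do not match. The window covers every adverse event, which under 6.1.1 includes intercurrent illness and injury. In the last 30 days of that window, the participant instruction covers only a subset, and the participant or a personal physician selects that subset before study staff hear of the event. Relatedness is better judged after an event has been collected. Here it acts as a filter on collection, applied by people who know which drug was taken, since 3.5.2 leaves participants unblinded.

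What is at stake is the completeness of the safety record. Section 6.3 provides no data safety and monitoring board and leaves monitoring to the PI, so oversight depends on what reaches that record. A team that follows the plan exactly would miss some events that the plan itself calls reportable.

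**Working it through.** The plan gives no figure to reproduce, so the check sets the sections side by side.

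**1. Is any contact planned in the 30 days?** Visit 5 is the last visit in 4.6 and in Table 3. Unscheduled contacts are tied to CGM problems. The 24-hour contact details given at the end of 4.6.5 are for questions during the CGM periods. The specific questioning of 6.2 happens at contacts, and none is planned after Visit 5. Planned active assessments in the window: 0.

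**2. What other routes exist after Visit 5, and what do they reach?**

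| Route | Section | Reaches a new event that nobody thinks related? |
|---|---|---|
| Participant self-report | 6.1.4 | No: limited to events believed related |
| Follow-up of unresolved events | 6.1.4 | No: the event began earlier |
| Investigator notice of deaths and events | 6.1.4 | No: limited to those that may be related |
| Notice of cancer or congenital anomaly | 6.1.4 | Only for those conditions, and only if the investigator learns of them |
| Later serious events | 6.2 | No: limited to those considered possibly related |
| Questioning at an unscheduled contact | 6.2, 4.6 | Only if such a contact happens |

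**3. Test case.** A participant is admitted for an acute illness 20 days after Visit 5, and nobody connects it with the trial. Under 6.1.3 it falls in the window. Under 6.1.6 an adverse event leading to hospitalization is documented and reported as serious; the listed exceptions turn on the reason for the admission, not on relatedness to the study. Under 6.1.4 the participant has not been asked to mention it, and no planned contact would bring it out.

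**4. Does a definition of the study period resolve this?** There are two readings of 6.2.

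- It includes the 30 days. Then 6.2 requires every event to be recorded, with no scheduled means of doing so and a participant instruction that is narrower.
- It ends at Visit 5. Then 6.2 covers only possibly related serious events afterwards, which is narrower than 6.1.3.

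Neither reading makes 6.1.3, 6.1.4, 6.2 and Table 3 agree.

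**5. Extent.** 24 participants (3.3) × 30 days (6.1.3) = 720 participant-days without a scheduled assessment, if all 24 complete Visit 5.

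**The case against.** The strongest reply is that 6.1.3 defines a reporting period and does not promise active solicitation. Section 6.3 sends the IRB only events with a reasonable possibility of being related, which fits the filter in 6.1.4. Section 6.1.4 is headed as post-study, and 6.2 also uses a related-only rule once the study period is over. If that period ends at Visit 5, then 6.1.4 and 6.2 are consistent with each other and only 6.1.3 needs clarifying.

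Part of this stands. An added call is one possible repair, and restating 6.1.3 is another. But the reply concedes that 6.1.3 as written goes further than the rest of the plan. The filter in 6.3 governs what is sent to the IRB; it does not tell participants which events to withhold from study staff.

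A reader might go further and infer four things that the documents do not support.

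- *That nothing else is collected after Visit 5.* The routes in 6.1.4 and 6.2 listed above exist, and any contact that does occur triggers questioning.
- *That the plan names a withdrawal risk at this point.* The remark on hyperglycemia in 3.2 explains why there is no wash-out between treatments. Section 3.5 limits the stopping of the previous sulfonylurea to the trial itself ("Throughout the 8 weeks (total) of this trial"), and treatment after Visit 5 is not described.
- *That one drug is favored.* The gap follows the second period, and order is randomized (3.5.1), so there is no systematic advantage to either drug. Section 5.1 plans no between-drug comparison of adverse events.
- *That about a third of events are missed.* From Visit 1, the tail is 30 / (56 + 30) = 34.9% of calendar days, with 8 weeks × 7 = 56. All of those days follow the end of study drug, and time from consent to Visit 1 would lower the share. It does not measure missed events.

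**Conclusion.** The concern holds as an inconsistency between stated rules. The plan makes all adverse events reportable through 30 days after the last visit, schedules no ascertainment of new events in that time, and gives participants a narrower instruction. The consequence is that new events thought unrelated, including admissions, can go unrecorded for 30 days in each of up to 24 participants. How many events that means cannot be derived from the documents.

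The conclusion rests on two readings: that Visit 5 is the last study visit for the purpose of 6.1.3, and that the reporting in 6.1.3 is not confined to what 6.3 sends to the IRB. If the second reading is wrong, the wording of 6.1.3 still needs correcting. Scheduled assessment at Visits 1 to 5, the primary outcome and the power calculation are unaffected. The matter should be settled, but it does not threaten the trial's main result.

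**What to change.** 1. In 6.1.4, instruct participants to report all events through day 30 after Visit 5, and apply the relatedness condition only to events after that.
2. Add to Table 3 one adverse event telephone contact at about day 30 after Visit 5, using the specific questioning already required by 6.2.
3. State in 6.2 that the study period runs through that contact.
4. Tabulate events with onset after Visit 5 separately from those during the two treatment periods.

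The cost is 24 short calls, one more column in Table 3 and about one month longer follow-up per participant. If the contact is not added, restate 6.1.3 so that the trial does not claim 30-day follow-up for all events, and define the study period to match.
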